In this 5-year NIH-funded research project (current NIH grant # R01MH123352), we propose an intervention entitled “WeTest-WeLink” that aims to (i) promote uptake of HIV self-testing among MSM in China, and (ii) linkage to care for MSM who obtain preliminary positive HIV self-test results. This proposal builds on years of formative work with MSM in China conducted by this team of investigators (previous NIH grant # R34MH106349), demonstrating promising effects from a pilot RCT and strong indication of intervention acceptability, feasibility, and cultural sensitivity. The intervention uses the “WeChat” mobile app platform, which offers multiple features built into the app that facilitate health information delivery and communication channels (e.g., capacity for private texts, group chats, video sharing, GPS, instant messaging, real-time audio and visual communication). This protocol is funded by the US National Institutes of Health, and includes three phases of research activity over 5 years. **Phase 1** (Year 1) involves use of online focus groups to refine the WeTest-WeLink intervention to incorporate additional and updated content regarding: the HIV care continuum, linkage to care for HIV-positive people and ART treatment; support and affirmation for those testing HIV-positive; and programming of GPS resources to assist participants in identifying care. Identification and incorporation of additional updated content will be guided by the Information-Motivation-Behavioral (IMB) theory of behavior change and Minority Stress Theory, and based on findings from focus groups to be conducted with MSM from study settings. **Phase 2** (Years 2-4) is a prospective 2-group RCT of 1,800 MSM recruited from 3 sites: Chengdu, Suzhou, Wuhan. Participants will be randomized to the control group or to the WeTest-WeLink intervention. Primary and secondary outcomes include: i) repeat HST at 6, 12, and 18-month follow-up, ii) linkage to care for those who test HIV-positive. Additional analysis will explore effects on behavioral HIV risk, engagement in HIV community-based prevention services, and theoretical mechanisms of behavior change. **Phase 3** (Year 5) involves qualitative examination with key constituents regarding implementation features specified within the CFIR.

RESEARCH PROTOCOL

Title: Mobile Health Intervention to Increase HIV Self Testing and Linkage to Services for High-Risk Men in China

Specific Aims

The overarching objectives for this R01 research project are to test the effectiveness of an mHealth intervention entitled “WeTest-WeLink” that will increase repeat HIV self-testing (HST) among MSM, and to examine the efficacy of “WeTest-WeLink” on linking individuals who test positive to HIV care. Based on a successful 3-year R34 NIMH-funded pilot study conducted in Hefei, Anhui Province, we established proof-of-concept for the use of the WeChat app to promote HIV self-testing with MSM. In the current 5-year R01 NIMH-funded research, we will employ a user-centered design process to refine and expand app features (e.g., app-based HIV and health promotion messages, videos, GPS maps, private groups and two-way communication channels) to support repeat HST uptake, behavioral risk reduction, stigma coping strategies, and self-efficacy to link to HIV care. With the goal of increasing sustainable behavioral changes and examining the scalability of this proposed intervention, we will subsequently conduct a formative evaluation on the implementation of the intervention. The goal of this R01 application will be accomplished by using an Effectiveness-Implementation Hybrid Type 1 design consisting of a three site, 2-arm RCT to quantitatively test the intervention’s effects on primary and secondary outcomes (repeat HST, linkage to HIV-related care) as well as qualitative research to examine implementation and scalability. We will recruit 1,800 HIV negative MSM, who will be allocated to the intervention (access to the WeTest-WeLink app) or control group (basic information about HST and passive referral to HIV care for individuals who test HIV positive). We will assess participants at 6-, 12-, and 18 months to measure intervention effects on primary outcomes: use of HST (including photographic confirmation) and linkage to care for individuals who test HIV-positive. Secondary outcomes include sexual risk behaviors and use of HIV prevention services, and we will conduct mediation analysis to examine theoretical mechanisms of behavior change. We will qualitatively assess intervention-related process characteristics that enable and/or impede implementation and scalability informed by the Consolidated Framework for Implementation Research (CFIR).

The aims of this 5-year research program are the following:

Specific Aim 1. To evaluate the effectiveness of the WeTest-WeLink intervention on HST behaviors

Hypothesis 1: Greater proportion of HST every six months, confirmed by photographic evidence of test results, in the intervention vs control group

Specific Aim 2. To evaluate the efficacy of the intervention on linkage to HIV related care

Hypothesis 2. Greater proportion of participants who test HIV+ in the intervention will be linked to care vs control group

Specific Aim 3. To inform broad scale implementation by assessing intervention barriers, facilitators, and potential adaptations for optimal uptake and sustainability

Hypothesis 3. Key informants will identify key intervention features that can enhance subsequent implementation and scalability in real-world, ecological settings

Background

Studies of MSM in China have found that stigma contributes to the underutilization of HIV prevention and testing services and to the underestimation of personal HIV risk behaviors. Many MSM refrain from accessing HIV prevention and testing offered through health clinics or local Centers for Disease Control (CDC) offices, out of fear of disclosing their same-sex behavior to physicians or CDC officials. A systematic review found that 62% of Chinese MSM had not been tested in the past 12 months and about half of them had never been tested for HIV in their lifetime. Low rates of testing and undiagnosed HIV infection pose substantial risks for furthering the growth of China's HIV epidemic. Interventions are urgently needed to increase rates of HIV testing for MSM in China as well as to facilitate linkage to care for those who test positive in order to disrupt the expanding epidemic in this population.

The use of mobile technologies to promote healthier behaviors ("mHealth") opens new avenues for support the use of HST. Emerging data suggest that delivery of HIV-prevention messages via mobile phone "apps" represents a feasible and acceptable way to encourage HIV testing and to lower HIV risk behaviors. In the context of HST, mobile phone apps can send text or video instruction on specimen collection and test result interpretation. In addition, automated app-delivered messages can provide timely, confidential, and convenient information to motivate risk reduction, retesting, and necessary referrals to care.

Preliminary Research

In our prior 3-year NIMH-funded project, we developed and pilot-tested the WeTest intervention to provide proof-of-concept for the use of WeChat to promote HIV self-testing. Development of WeTest involved iterative rounds of quantitative and qualitative research with MSM in China to identify intervention targets and MSM-sensitive delivery processes for app-based HIV communication, messaging, and referrals. WeChat development was based on the Information-Motivation-Behavior (IMB) theory, a widely accepted, evidence-based approach to promoting HIV-related behavior change. In accordance with this theory, WeChat provided accurate and up-to-date HIV prevention information (about HIV transmission, prevention strategies, testing recommendations, living with and treatment for HIV, local HIV epidemiology in MSM populations), messages and stories to motivate risk reduction, and guidance and self-efficacy to engage in risk reduction behaviors. In addition, WeChat was informed by Minority Stress Theory, a framework that explicates the role of social stigma as a factor contributing to maladaptive health behaviors, including risk for HIV transmission in MSM. In accordance with this theory, WeChat included messages and short articles (vignettes, first-person narratives) to support participants' MSM identities and affirm their same-gender sexuality, used empowering language, and provided information/referrals regarding local MSM-serving NGOs that advocate for the needs of this population. WeChat offered standard content – videos, fact sheets, local linkage/referral information, two-way communication feature – which was permanently available on the main WeChat landing page. WeChat also sent two additional weekly messages to participants' "message feed" – including brief informational articles about HIV, STIs, and HIV testing; first-person stories about people living with HIV; local data about HIV and STI infections among MSM; news about national policies related to HIV; and stories about general health concerns of MSM – drawn from a library of pre-prepared messages/stories for this project.

Over a 3-month outreach and recruitment period, the study team recruited and enrolled 100 MSM participants into the pilot RCT and examined the acceptability, feasibility, and 6-month outcomes on HIV testing and condom use. All participants enrolled (100%) were retained at 6-month follow-up. At follow-up, participants in the intervention group had increased uptake of oral HST following baseline procedures (adj. RR=2.17, 95%CI: 1.08-4.37) and increased trust in use of oral HST (adj. RR=2.28, 95%CI: 1.15-4.51), compared to the control. Nearly all (98%) of those who reported using HIV self-test kits uploaded and submitted photographic confirmation of their test

results to study staff via the secure WeChat project portal. This high submission rate is indicative of the potential utility for remote health workers to counsel, refer, and provide linkages to care for people who test positive. Overall, 10 individuals tested positive and all received immediate linkages to care. In qualitative exit interviews, intervention participants commented favorably about app-based approach for supporting HST and prevention, the ability to communicate with online remote counselors for questions and referrals, the discrete nature of the app as a way to avoid uncomfortable disclosure, and the focus on MSM-based support and identity affirmation. These results provide compelling support for the feasibility and acceptability of WeTest, and demonstrate the team's ability to recruit and implement a mHealth intervention for this population.

Methods

This 5-year project involves 3 phases of research.

Phase 1 involves use of online focus groups to refine the WeTest-WeLink intervention to incorporate additional and updated content regarding: the HIV care continuum, linkage to care for HIV-positive people and ART treatment; support and affirmation for those testing HIV-positive; and programming of GPS resources to assist participants in identifying care. **Phase 2** is a prospective 2-group RCT of 1,800 MSM. Participants will be randomized to the control group or to the WeTest-WeLink intervention Primary and secondary outcomes include: i) repeat HST at 6, 12, and 18-month follow-up, ii) linkage to care for those who test HIV-positive. Additional analysis will explore effects on behavioral HIV risk, engagement in HIV community-based prevention services, and theoretical mechanisms of behavior change. **Phase 3** involves qualitative examination with key constituents regarding implementation features of the program.

Recruitment and retention:

We will recruit participants using the following strategies:

1. In-person Recruitment. Study staff will approach men in known venues identified in previous research where the target population congregates (e.g., bars, cafes, bookstores). They will take individual men aside and tell them about the study, provide small study cards or fliers to interested individuals, and encourage them to contact the study office if interested. If an individual is interested and wants to set up an appointment, study staff will schedule a time for the intake.

2. Online Recruitment. Study recruitment staff will create profiles on known websites in China where members of the local target population spend time (e.g., Blued, Aloha), following recruitment procedures used successfully in the team's previous research with MSM in China. They will identify themselves as conducting a men's health study. If a member of the target population approaches study staff online, they will explain the project, and will offer to do a screener over the phone. If the potential participant is eligible, they will schedule an intake appointment with a member of the study staff.

3. Community-based Referrals. Study recruitment staff will make presentations about the study to staff at relevant community-based organizations and service agencies in each target city. They will discuss the general study, and will also leave recruitment materials. They will ask staff to refer potential participants to the study by giving men the recruitment materials and encouraging them to contact study staff if interested.

Phase 1 (Year 1): Intervention update and refinement.

The purpose of Phase 1 is to update and refine the intervention content using focus groups, which will allow us to expand app features (e.g., app-based HIV and health promotion messages, videos, GPS maps, private groups and two-way communication channels) to support uptake and repeat use of HST, behavioral change, stigma coping strategies, and self-efficacy to link to HIV care. All focus group discussions will be conducted using remote online procedures (via WeChat or Zoom).

Participants. We will conduct 12 focus groups total – 4 focus groups per research site (Chengdu, Suzhou, Wuhan). (i) We will conduct 6 focus groups with HIV-positive MSM (2 focus

groups per site; n=4 participants per group). (ii) We will also conduct 6 focus groups with HIV-negative MSM (2 focus per groups; n=4 per group) (48 Phase 1 participants total). Due to concerns related to COVID-19, focus groups will occur via the Internet.

Participants must be: aged 18 years or older; possess a mobile “smart” phone; experienced using WeChat; had condomless anal sex with another man in the past 6 months; reside in the site for at least 6 months. HIV-positive MSM focus groups will discuss their experiences receiving an HIV-status diagnosis, linkage to care, stigma coping and support needs. HIV-negative MSM focus groups will discuss anticipated challenges in repeat HST, anticipated barriers to care, risk reduction, and stigma coping and support needs. Additional focus groups may be held depending on need for data saturation. We will attempt to maximize diversity within focus groups in order to represent MSM of varying ages, education levels, and prior engagement in HIV prevention/testing. Eligible participants will receive a detailed description about the study and complete informed consent procedures. HIV-positive participants will be informed that participation will involve discussing their HIV status in the presence of other HIV-positive MSM; they will be given the option to complete individual interviews upon request.

Procedures. Individuals who respond to recruitment efforts will be screened by a project staff member, using either the WeChat calling feature or at an in-person meeting at a collaborating NGO project office. Those ineligible will be excused and receive an electronic link or physical brochure with referrals to health services and recommendations about HIV prevention and testing. Those eligible will continue with the procedures described here. Focus groups participants will be sent an invitation to a secure online/internet platform. We will begin focus groups with a demonstration of two videos that will be provided as standard content in the WeChat-WeLink app group. The first brief video, developed for use in the R34 pilot study, demonstrates use of the locally manufactured HIV-1/2 oral self-test test kits (ABON Biopharm Co. Ltd, in Hangzhou). ABON oral HIV self-test kits have 100% initial sensitivity and 99.7% specificity, and are endorsed for use by USAID and the Global Fund. The video demonstrates how to self-administer the testing device (using an oral swab, no blood required); the importance of checking for expiration date (typically two years from purchase); how to interpret the test results; what to do if results are positive; how to safely dispose of the testing device (a package for safely disposing the device is included in the kit). We will provide a second brief video demonstration about the importance of linking to an HIV care site after testing HIV-positive. This video addresses myths and stigma about receiving an HIV-positive diagnosis, and emphasizes linkage to care as a step toward obtaining ART medication and achieving viral suppression. The video will clarify that ART is provided free through the local CDC, and will underscore the importance of communication with providers, medication adherence, attendance at follow-up clinic appointments and the importance of viral suppression to minimize risk of transmission to others.

Focus group discussions will explore the appropriateness, relevance, and fit of the videos to population experiences and needs. Additional aspects of the WeChat platform and library of pre-prepared content will be presented: local linkage/referral information to MSM-affirming NGOs and health promotion sites; brief informational articles about HIV, STIs, and HIV testing; first-person stories about people living with HIV; local data about HIV and STI infections among MSM; news about national policies related to HIV; and stories about general health concerns of MSM. Focus group facilitators will encourage participants to consider strategies for improving and updating the video content, and will solicit input on additional videos, brief messages, fact sheets, vignettes/stories, and referral sites. We will demonstrate the two-way communication features, which will facilitate engagement with a study staff member for deeper advice or support, and we will demonstrate the GPS feature, which will facilitate location of and linkage to CDC offices and care clinics, local MSM-affirming NGOs, and other HIV prevention/education sites. We will ask focus group participants to consider the necessary forms of information, motivation, and behavioral skills as well as stigma coping strategies to support repeated HST and linkage to care. Focus groups facilitated by trained members of co-I [name] study team, will be audio recorded and participants will be compensated with 150 RMB (approximately 20 USD). An additional trained staff member will observe the discussions and take detailed notes from the

focus groups sessions, which will be summarized to reflect preferences and recommendations about message content, components, and delivery.

Qualitative Analysis. Audio recordings will be transcribed into Mandarin and translated into English by professional translation services. Following Braun and Clarke's thematic analysis framework, a team of coders will independently read the transcripts and convene regularly to discuss emerging themes. The coding process will begin with the team reading each participant interview multiple times in order to become familiar with the data. This will be followed by indexing themes and categories. All the data relevant to each category will be identified and labelled to establish categories using a systematic approach. MAXQDA software will be used for cross-indexing, sharing, and managing the data. At the conceptual level, analysis involves identification and summarizing patterns of experience related to HST self-administration, perceived facilitators and barriers to linkage to care, and preferences regarding app-based messages. At the descriptive level, the analysis involves identifying a diverse range of brief messages that can be delivered via mobile apps for motivating and encouraging repeat HIV testing and linkage. In addition, multiple coders will analyze subsets of the data and inter-rater reliability will be assessed; discrepancies will be resolved with discussion.

Based on findings from focus groups, we will update/enhance WeChat content, create/program new content, and compile additional resources that support repeat HST, linkage, and risk reduction.

Potential Risks and Benefits

1. There is a risk of loss of privacy or confidentiality of data, including sensitive data on sexual behaviors and psychological characteristics. We take this risk seriously, and we will take steps to protect participants' confidential data and anonymity. We will ensure that personal identifiers are removed from the data and any publications arising from the study. The informed consent documents will bring confidentiality risks to participants' attention. We will encourage participants to not disclose any content of the focus group discussions.
2. Participants may experience psychological discomfort while completing qualitative procedures, which will involve discussion or disclosure about HIV testing, sexual behavior, HIV status, and physical health. We will take steps to minimize any psychological discomfort. Research staff members will prepare a list of referrals to address potential psychological problems in the target populations.
3. The risk of loss of privacy will be controlled (as described above) by using unique participant ID numbers on all data rather than participant names. During the focus groups, participant will be informed that they can use a pseudonym in order to keep their identity/name unknown in the group discussions. We will develop a MOU with a professional transcription agency to assure that all names or identifiers are omitted from the transcripts, and that security protocols of all data recordings are maintained. Research staff be trained on confidentiality issues. Only essential staff members will have access to data and research files.
4. Participants may not receive any benefit for participating in this research project other than having the opportunity to learn more about HIV self-testing and HIV-related sex risk behaviors. This may lower their chance of exposure to HIV and other sexually transmitted infections in the future.

Inclusion of Women and Minorities

All (100%) of the participants will be males ages 18 and over. In accordance with the research aims, 100% of participants will be non-White racial/ethnic minority individuals. All (100%) of the participants will be Chinese (Asian).

Confidentiality

In order to protect study participants from potential risks related to the breach of confidentiality, the following steps will be taken: 1) All information provided by the participant will be referenced to a participant ID# and will be kept in locked file cabinets. The patient's ID# can be connected to the participant's name only through a single master file, accessible only to authorized senior research staff and kept locked in a file separate from the data files. All data files entered on computers will be protected by passwords and computer disks will be maintained in locked file cabinets. 2) All research staff will be trained in the importance of maintaining confidentiality of the information obtained from patients and will undergo the mandatory NIH training in protection of human research participants. 3) All data collected from the participants will be presented in aggregate form and no participants will be identified individually.

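### Does the self-testing endpoint need a stated rule for windows that follow a positive HIV result?

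*Combined protocol and SAP*

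**What the plan says.** Hypothesis 1 under Specific Aim 1 is "Greater proportion of HST every six months, confirmed by photographic evidence of test results, in the intervention vs control group". The Specific Aims text sets assessments at 6, 12 and 18 months and names two primary outcomes: "use of HST (including photographic confirmation) and linkage to care for individuals who test HIV-positive". The cohort is described in the same place: "We will recruit 1,800 HIV negative MSM". The opening project summary frames the second aim as "linkage to care for MSM who obtain preliminary positive HIV self-test results", and the Methods overview of Phase 2 lists "repeat HST at 6, 12, and 18-month follow-up".

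None of these places gives the denominator of the self-testing proportion or the status of a man in windows after a positive test. They also do not say whether a preliminary or a confirmed positive would matter. The detailed methods in the document cover the Phase 1 focus groups. Phase 2 appears only in outline, with no significance level, power, model, target effect or missing-data rule.

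**The concern.** Linkage to care has no data unless some men test positive during follow-up, so this event is expected. A man who knows he is positive has little reason to self-test again. An arm that tests more will also find such men sooner, so the event depends on treatment.

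Three rules are plausible for his later windows:

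- count them as not tested;
- remove him from the at-risk set;
- count them as met.

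If he is kept as a non-tester, an effective intervention is penalised for the infections it detects. If his windows count as met, an arm that only found more infections early can look better later. Once positives per arm are known, the direction in which each rule moves the comparison can be foreseen. An unstated rule therefore leaves room for a choice made after seeing data on a primary outcome.

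**Working it through.** The document gives no design figure to reproduce: 1,800 is stated without a control rate, effect or power. The check is therefore how far the three rules can differ.

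**Inputs.** From the document: three six-month windows, 1,800 men HIV negative at entry, and a pilot adjusted relative risk of 2.17 for uptake of self-testing (Preliminary Research). Assumed: 900 per arm; 50% vs 65% testing per window among men not yet diagnosed; a share *i* newly infected at the start of each window; no testing after diagnosis.

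**Formulas.** Let *p* be the testing rate and *D* the share diagnosed before the window. The observed proportion is *p*(1 − *D*) if later windows count as not tested, *p* in the at-risk set, and *p*(1 − *D*) + *D* if they count as met.

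**Worked case, *i* = 2%.**

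- Before the 12-month window: *D* = 0.50 × 0.02 = 0.0100 (control) and 0.65 × 0.02 = 0.0130 (intervention). Not tested: 0.65 × 0.9870 − 0.50 × 0.9900 = 14.66 points.
- Before the 18-month window, control: 0.0100 + 0.50 × (0.0100 + 0.0196) = 0.0248. Intervention: 0.0130 + 0.65 × (0.0070 + 0.0196) = 0.0303. Here 0.0196 is 2% of the 98% still uninfected.
- At 18 months, not tested: 0.6303 − 0.4876 = 14.27 points. Met: 0.6606 − 0.5124 = 14.82 points.

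| New infections per window | 12 months: not tested / at risk / met | 18 months: not tested / at risk / met |
|---|---|---|
| 1% | 14.83 / 15.00 / 14.98 | 14.63 / 15.00 / 14.91 |
| 2% | 14.66 / 15.00 / 14.96 | 14.27 / 15.00 / 14.82 |
| 5% | 14.14 / 15.00 / 14.89 | 13.20 / 15.00 / 14.55 |

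At 6 months *D* = 0 under every rule. With 900 per arm, power for 15 points stays near 100%. For a 5-point effect, which the document does not target, scoring as not tested at 2% lowers power at 18 months from 57% to 53%.

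**Do the rules err in opposite directions?** Not in the table, where both whole-cohort rules fall below 15. They do if the effect is confined to the first window, for example 40% vs 75% and then 50% in both arms. At *i* = 2%, *D* is 0.008 vs 0.015, so the 12-month difference reads 0.50 × (0.008 − 0.015) = −0.35 points as not tested, +0.35 as met, and 0 in the at-risk set.

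**Is the at-risk set the safe choice?** It is exact above only because all men share one testing rate. Suppose instead that half the men test at 10% and half at 30%. The pilot relative risk raises these to 21.7% and 65.1%, a true difference of 43.4% − 20.0% = 23.4 points. Frequent testers carry three times the infection risk, so at an average of 2% per window the halves have 1% and 3%.

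- Diagnosed before the 18-month window: control 0.0029 and 0.0240, mean 0.0135; intervention 0.0060 and 0.0453, mean 0.0257.
- Tested, as a share of all men: control ½(0.10 × 0.9971 + 0.30 × 0.9760) = 0.1963; intervention ½(0.217 × 0.9940 + 0.651 × 0.9547) = 0.4186. As not tested the difference is 22.24 points.
- At risk: 0.4186/0.9743 − 0.1963/0.9865 = 23.07 points. Met: 0.4443 − 0.2097 = 23.45 points, both from unrounded values.

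With 5% new infections per window, the at-risk set reads 22.56 and met reads 23.53. With 2% new and 10% infected at entry (5% and 15% in the two halves), they read 22.10 and 23.41. Exclusion is then the worse of these two, by up to 1.3 points from the truth.

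**The case for a change.** The strongest case for acting is that the event is certain to occur, depends on arm, touches a primary outcome, and would take only a sentence or two to settle before the data are seen. The sizes can also be larger. If 10% of enrolled men had undiagnosed infection, with 2% new per window, the true 15 points would read 12.39 as not tested and 14.16 as met at 18 months. The pilot reported 10 positives among 100 men.

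Part of this stands. The rule is absent from the text, and deciding it before unblinding is good practice.

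The 10% case is an upper bound. The pilot account gives neither the timing nor the arm of its positives, and this trial enrols men described as HIV negative. Even so, a 10-point effect (50% vs 60%) with 10% infected at entry and 2.5% new per window reads 8.2 points as not tested at 18 months, and power is still about 0.94 against 0.99.

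Triggering exclusion on the positive photograph is no clean answer either. The pilot's "Nearly all (98%) of those who reported using HIV self-test kits uploaded and submitted photographic confirmation" is not split by arm or by result. A man diagnosed at a clinic or local CDC office leaves no such photograph and would stay in the set as a non-tester. Some exclusions would also be false positives. The kit figures under Phase 1 Procedures, "ABON oral HIV self-test kits have 100% initial sensitivity and 99.7% specificity", imply, if the same kit is used, 900 × 0.50 × 2 × 0.003 = 2.7 control and 900 × 0.65 × 2 × 0.003 = 3.5 intervention false positives before the third window.

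**Conclusion.** No change to the plan follows. This is a missing detail in a summary of Phase 2, of the kind an analyst must settle in any case when writing down the denominator. A fuller Phase 2 analysis plan may exist elsewhere. No stated rule produces a wrong result.

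For men uninfected at entry, with 50% vs 65% testing and 1% to 2% new infections per window, scoring later windows as not tested costs 0.2 to 0.3 points at 12 months and 0.4 to 0.7 at 18 months, out of 15. The met rule costs at most 0.2. Opposite errors arise only in some patterns, such as an effect that fades after the first window.

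The choice between rules is a fair trade-off. The at-risk set is formed after randomisation, and when testing habits and infection risk go together it can be off by about 1 point while the met rule is nearly unbiased. With a common testing rate the order reverses.

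All of this rests on assumed rates and on reading the endpoint as a separate proportion in each window. If it means testing in every window, these figures do not carry over.

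### Could scoring only photo-confirmed self-tests let a difference in uploading pass for an effect on testing?

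*Combined protocol and SAP*

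**What the plan says.** The self-testing outcome is worded in three ways.

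- Hypothesis 1, under Specific Aim 1: "Greater proportion of HST every six months, confirmed by photographic evidence of test results, in the intervention vs control group".
- The overview paragraph of the Specific Aims: "primary outcomes: use of HST (including photographic confirmation) and linkage to care for individuals who test HIV-positive".
- The opening summary, repeated in the Methods: "Primary and secondary outcomes include: i) repeat HST at 6, 12, and 18-month follow-up", without mention of a photo.

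The arms differ in contact with the study. The intervention arm has the WeTest-WeLink app, which the Phase 1 Procedures describe as having "two-way communication features, which will facilitate engagement with a study staff member for deeper advice or support". The Specific Aims overview describes the comparator as a "control group (basic information about HST and passive referral to HIV care for individuals who test HIV positive".

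The only upload route described is the pilot's, under Preliminary Research: "Nearly all (98%) of those who reported using HIV self-test kits uploaded and submitted photographic confirmation of their test", sent as "results to study staff via the secure WeChat project portal". The pilot figure is not split by arm. For the RCT, the text available names no upload route for either arm and gives no rule for a reported test without a photo.

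**The concern.** If a test counts only when a photo arrives, a man who tests but sends no photo is scored as not having tested. Suppose testing is the same in both arms and uploading is not. The observed rates then differ, and the rate ratio equals the ratio of the two upload rates. More staff contact in the intervention arm makes a gap in its favour conceivable. With 1,800 men the trial can detect small differences, so a modest upload gap could push a null comparison towards significance.

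The looser wordings add a second doubt: two analysts might disagree on whether an unphotographed test counts. Prompts also cannot be equalised once follow-up is over, so the point seems worth settling early.

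**Working it through.** **Inputs from the documents.** Total sample size 1,800. Pilot: 100 men, 98% of reported kit users uploaded, adjusted RR for self-testing 2.17 (95% CI 1.08 to 4.37).

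**Assumptions, because the documents give no figure.** 1:1 allocation (900 per arm); two-sided 5% test at one time point; the same true testing rate *t* in both arms. For the pilot: equal arms, with the adjusted RR treated as crude. The plan states no figure on this point, so there is none to reproduce.

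**Step 1. Could pilot controls upload?** The control share of kit users is 1/(1 + RR).

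- RR 2.17: 1/3.17 = 0.315, so the intervention share is 0.685.
- RR 4.37: 1/5.37 = 0.186, so the intervention share is 0.814.

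Had controls had no way to upload, overall uploading could not have exceeded about 68% (81% at the upper limit). The reported figure is 98%. Read as all users, which is what the sentence says, controls did upload.

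**Step 2. The largest gap that fits 98%.** Put every missing photo in the control arm: control upload = 1 - 0.02/share.

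- RR 2.17: 1 - 0.02/0.315 = 0.937, against 100%. Spurious RR = 1/0.937 = 1.07.
- RR 1.08: share 1/2.08 = 0.481; upload 0.958; spurious RR 1.04.
- RR 4.37: upload 1 - 0.02/0.186 = 0.893; spurious RR 1.12.

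Put every missing photo in the intervention arm instead: 1 - 0.02/0.685 = 0.971 against 100%, a ratio of 0.97. The bias then works against the intervention.

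**Step 3. A plausible range for *t*.** With RR 2.17 taken as crude, the pilot control rate cannot exceed 1/2.17 = 46%. The trial's rate may differ, so 70% is shown as well.

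**Step 4. False significance when testing is equal.** The observed rates are p1 = *t* × intervention upload and p2 = *t* × control upload. With pooled rate p = (p1 + p2)/2, s0 = √[2p(1 - p)/n] and s1 = √[(p1(1 - p1) + p2(1 - p2))/n], the chance of rejection is Φ[(d - 1.96 s0)/s1] + Φ[(-d - 1.96 s0)/s1], where d = p1 - p2.

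Worked case, *t* = 0.30 and 100% against 93.7%: p1 = 0.300, p2 = 0.281, d = 0.019, s0 and s1 both about 0.0214. The two terms are 0.142 and 0.002, which sum to 0.144.

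| Upload, intervention vs control | Spurious RR | *t* = 30% | *t* = 46% | *t* = 70% |
|---|---|---|---|---|
| 98% vs 98% | 1.00 | 5% | 5% | 5% |
| 98% vs 95% | 1.03 | 7% | 9% | 16% |
| 100% vs 93.7% (pilot worst case) | 1.07 | 14% | 24% | 52% |
| 98% vs 90% | 1.09 | 20% | 35% | 71% |
| 97.1% vs 100% (reverse) | 0.97 | 7% | 9% | 16% |

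The spurious difference is *t* times the upload gap. It is 0.9 to 2.1 points for 98% against 95%, and 2.4 to 5.6 points for 98% against 90%, over *t* = 30% to 70%. At 720 per arm (20% loss assumed) the chances fall to 7-14% and 17-61%.

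**Step 5. The wordings side by side.** Hypothesis 1 requires a photo. The overview's phrase reads naturally as self-testing with a photo. The summary and the Methods give the behaviour and its timing in shorthand and exclude nothing. The specific statement governs the general ones, and an analyst following Hypothesis 1 contradicts none of them.

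**The case for a change.** The strongest reply is that the pilot reassures only so far. Its 98% comes from the kit users among 100 men, followed for 6 months with complete retention, and it is not split by arm. The trial enrols 1,800 men for 18 months, over which uploading could fall, and could fall further where contact is thinner. At the upper confidence limit of the pilot RR, the worst-case control upload is 89% and the spurious ratio 1.12. Testing rates above 46% cannot be excluded either, and the false-positive rates climb steeply there.

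Part of this stands. The text does not state a common route or common prompts, and the 98% need not carry over. But the worst case needs every missing photo to fall in one arm, and nothing in the documents puts it there. Nothing says that controls are denied the portal, which is described as belonging to the project and not as intervention content. The highest error rates need 70% testing, which no figure in the documents supports.

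The silence is also of a general kind. The text available gives procedures for the Phase 1 focus groups and only outlines the RCT, and some pages were removed before review. An upload route not written there is no sign that the arms are handled differently.

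Reporting upload rates by arm, or adding a supportive analysis of self-reported testing, would be informative. Neither would alter the primary outcome or the claim. Self-report is itself open to over-reporting, possibly more so among men who know they receive the intervention, so agreement between the two analyses would not rule out bias.

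**Conclusion.** The concern does not call for a change. The mechanism is real as arithmetic, but the documents do not show that the arms would upload differently, and the one precedent they offer suggests that both arms could upload at high rates. Run with the pilot's portal and an upload rate near 98% in both arms, the photo-confirmed comparison is sound, with the false-positive rate at 5%.

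In the pilot's worst case the distortion is a rate ratio of about 1.07 (1.04 to 1.12 across the confidence interval of the pilot RR), against a pilot effect of 2.17. It could run in either direction. It could not account for an effect of the pilot's size, though it could blur a very small one.

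Requiring a photo is a fair trade: it accepts some missed tests to guard against over-reported ones. Whether an unphotographed test counts is answered by Hypothesis 1, and the shorter wordings fit that reading. A shared upload route and equal prompts are details that a competent trial team would settle in its RCT procedures.

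This conclusion rests on reading the 98% as covering both pilot arms, on equal pilot arms with the adjusted RR taken as crude, and on 1:1 allocation in the trial.
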